6.11.4.4 Additional Analyses

No subgroup analysis is planned and any proposed subgroup analyses will be agreed with the appropriate governance committees.

6.11.5 Analysis Population and Missing Data

The exploratory efficacy analyses will be on the 'Intention-to-treat' population, i.e. as per randomisation rather than intervention actually received. There are no plans to impute missing data, i.e. these analyses will be on a 'complete case' basis.

6.11.5.1 Economic evaluations

This will explore the feasibility of collecting resource use and quality of life data, to inform the design of the health economics component of a future definitive trial.

Estimation of cost-effectiveness, within a health-technology assessment, is an iterative process⁴⁹. In this trial we aim to monitor levels of resource-use and quality of life (QoL), to inform the decision as to how costs and benefits should be measured as part of a future, more definitive study.

NICE guidance⁵⁰ recommends that costs are calculated from the perspective of the NHS and personal social services (PSS). However, it is acknowledged that not all cost data can be collected, and it is suggested that the focus be on large cost drivers and those costs that are likely to differ between arms⁵¹. We will thereby seek to monitor levels of resource-use associated with the intervention and standard care arm of the study.

Intervention - Serial use of MRI at 3, 6, 9 and 12 months to identify disease resolution and thus discontinue immobilisation

Standard Care - Immobilisation discontinued on the basis of clinical remission determined by skin temperature measurement

Data on other primary, and secondary care visits and admission to hospital will be collected. This information will be extracted using a patient diary and secondary care notes. Time off work and levels of informal care will also be monitored. Appropriate unit costs will subsequently be attached to all items of resource-use⁵².

In line with guidance⁵⁰ the EQ-5D-5L⁵³ will be used to measure quality of life (QALY (Quality Adjusted Life Year) scores can be calculated from the EQ-5D⁵⁴. Participants will be asked to complete the EQ-5D-5L at 3 months, at 6 months, 9 months, 12 months, 1 month after remission, and at 6 months post remission

6.11.5.2 Health Economic Analysis Plan

The main purpose of the analysis is to inform how the above data on costs and effects would be collected within a more definitive study. Thus, we will estimate completion rates and seek to identify big cost drivers, in order to inform this decision. Additionally, though the results of this will need to be treated with caution, a preliminary cost-effectiveness analysis will also be performed. As such, we will estimate the mean incremental cost and mean QALY gain associated with the intervention compared to standard care.

6.12 Data Monitoring

6.12.1 Data Monitoring Committee

This has been assessed as a low risk trial.

6.12.2 Interim Analyses

No interim analyses is planned

6.12.3 Data Monitoring for Harm

The TMG will be provided with safety data from each treatment arm about any adverse event related to the monitoring carried out as part of the trial. The TMG will make recommendations to the Trial Sponsor on the continuation or early stoppage of the trial in the unlikely event that there are concerns over harm to participants.

6.12.3.1 Safety reporting

The intervention in the trial is increased frequency of MRI scanning which is compared with standard care of MRI scanning to confirm resolution of following temperature assessment of the affected limb. Contrast is not used for MRI scans in this study. Thus a pragmatic approach to safety reporting will be used. MRI scans are being performed in NHS trusts under routine clinical protocols. Adverse incidents resulting from MRI scans will be reported by the research site in line with the trusts clinical incident reporting policy. A copy of the incident form will be forwarded to the CI of the trial as soon as practicable. They will be forwarded to the Trial Sponsor on receipt by CI and will be reviewed by the TMG.

The following anticipated events are recorded as secondary outcomes. They will be reported as clinical events and reviewed by the TMG.

CN -RELATED SAFETY OUTCOMES

- Worsening of existing ulceration
- Infection of an ulcer
- Secondary ulceration on either limb
- Major and minor amputation
- Increase in pain

Off-loading – RELATED SAFETY OUTCOMES

- Falls as a consequence of wearing the off-loading device
- Iatrogenic skin irritation or lesions from off-loading device

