6.5.2 Exploratory Clinical Outcomes

- Days with immobilisation, measured at the end study
- Progression of foot deformity as documented by measuring radiological foot alignment angles. All x-rays will be taken in a weight bearing position with standard views as per WPD. Comparison from baseline, diagnosis of remission, and six months after remission. The angles that will be assessed are:
 - Calcaneal Inclination – the angle formed by the horizontal and a line from the base of the heel and inferior cortex of the calcaneus
 - Talar Declination – the angle between the line originating from the centre of the talus bisecting the talar neck and head and the weight bearing plantar surface from the calcaneus to the 5th metatarsal
 - Talo-first metatarsal angle – the angle between the line originating from the centre of the talus bisecting the talar neck and head, and the line through the longitudinal axis of the first metatarsal.

- Hindfoot-forefoot angle - the angle between the talocalcaneal bisector and the second metatarsal shaft
- Cuboid height (mm) - the distance from the plantar aspect of the cuboid to a horizontal line drawn from the plantar calcaneal tuberosity to the fifth metatarsal head.

Patients who have undergone previous minor amputation and/or previous orthopaedic surgical fixation of the foot altering/removing the anatomical landmarks of the foot will be excluded from this analysis due to the absence of bony landmarks.

At each study visits the following will be measured and recorded on the eCRF:

- Number of new ulcerations on the index foot
- Number of new ulcerations on the contralateral foot
- Number of new infections on the index foot
- Number of new infections on the contralateral foot
- Number and severity of falls (Hopkins Fall Grading System)¹
- Number of minor and major amputations on the index foot at the end of the follow up phase of the study
- Number of minor and major amputations on the contralateral foot at the end of the follow up phase of the study
- The number of participants in each arm requiring further intervention for CN (e.g. further immobilisation) within 6 months of remission

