6.6 Participant Timeline

	Active Phase (fortnightly visits throughout active phase of trial)										Remission	Follow Up after remission diagnosed			
Visit Number	1		6		11		18		25			FUV1	FUV2	FUV3	FUV4
month			3m		6m		9m		12m			1month	2months	3months	6months
Week **	0	2 weekly	W12	2 weekly	26	2 weekly	40	2 weekly	52						
Check In/exclusion criteria *	*														
Hand out FIS *	*														
Consent *	*														
Randomisation *	*														
Medical History *	*														
Foot Surgical history *	*														
Medication *	*	*	*	*	*	*	*	*	*	*	*	*	*	*	*
Record any amputation/s *	*	*	*	*	*	*	*	*	*	*	*	*	*	*	*
Record any infection/s *	*	*	*	*	*	*	*	*	*	*	*	*	*	*	*
Record any ulceration/s *	*	*	*	*	*	*	*	*	*	*	*	*	*	*	*
Record any falls *	*	*	*	*	*	*	*	*	*	*	*	*	*	*	*
Hand out patient diary *	*	*	*	*	*	*	*	*	*	*	*				
Collect & upload diary *		*	*	*	*	*	*	*	*	*	*				
Foot temperatures *	*	*	*	*	*	*	*	*	*	*	*	*	*	*	*
MRI (usual care) **	*									*					
MRI (Intervention arm) **	*		*		*		*		*						
Classification *	*														
Neuropathy Assess *	*														
Vascular Assess *	*														
BMI *	*		*		*		*		*		*				*
HbA1c (use existing if <3months) *	*														
Pain VAS *	*		*		*		*		*		*				*
HADS *	*		*		*		*		*		*				*
SF-12 *	*		*		*		*		*		*				*
EQ5D *	*		*		*		*		*		*				*
Study specific X-ray															*
		← Duration of active phase of treatment will be variable →													
Patient Interviews		← →													

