6.7.4 Follow up phase

In both arms once remission is confirmed by the MRI patients will then enter a rehabilitation/weaning phase. They will be transferred into a less restrictive off-loading device and then finally into footwear as per standard care. Participants will continue to attend for monthly trial visits for 3 months to monitor for any sign of relapse. The final visits will be at 6 months post remission. Standard care will continue to be provided.

At each visit study specific procedures will be carried out:

- The temperature will be assessed as per the WPD
- The participant diary will be collected and another issued for participants to complete until their next study visit. (This is only for the first three follow-up visits)

In addition to standard care and study specific procedures the participant will be asked to complete the following questionnaires and additional tests/investigations:

Follow Up - Month 1: VAS, SF-12, HADS and EQ-5D-5L will be completed.

Follow UP Month 6: VAS, SF-12, HADS and EQ-5D-5L completed. BMI will be recorded and an X-ray of the foot and/or ankle will be taken.

Relapse will be defined as a temperature difference of $>2^{\circ}\text{C}$ compared to the contralateral foot maintained for two or more occasions or further changes on imaging¹⁵. As per standard care the final decision as to whether the participant has relapsed will be at the discretion of the clinic team. If this occurs, then the participant will then recommence off-loading with a non-removable device. They will continue to be followed up as per the study protocol.

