6.12.4.4.2 Trial Management Group

A Trial Management Group (TMG) will be set up to assist with developing the design, co-ordination and strategic management of the trial. The membership, frequency of meetings, activity (including trial conduct and data review) and authority will be covered in the TMG terms of reference.

The TMG will review serious clinical incidents associated with MRI scanning and adverse events described in 6.13.3.1 to

- Detect any trends, such as increases in un/expected events, and take appropriate action
- Provide advice to the CI to when to seek information from investigators where required
- Provide advice to Sponsors on the risk of the trial continuing and take appropriate action where necessary

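### The falls entry on the safety list in 6.12.3.1 is narrower than the all-falls outcome it is said to repeat, so falls in footwear are not on the list the Trial Management Group reviews

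*Protocol*

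**What the plan says.** Section 6.12.3.1 introduces its safety list with "The following anticipated events are recorded as secondary outcomes. They will be reported as clinical events and reviewed by the TMG". Under the off-loading heading, the only entry on falls is "Falls as a consequence of wearing the off-loading device".

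The outcome sections set no such condition. Section 6.5.2 has "Number and severity of falls (Hopkins Fall Grading System" under the instruction "At each study visits the following will be measured and recorded on the eCRF". The 6.6 timeline has a row "Record any falls", marked through the active phase, remission and the follow-up visits. Section 6.11.4.2 counts falls over the whole study period.

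Two other sections say what reaches the TMG. Section 6.12.3 says "The TMG will be provided with safety data from each treatment arm about any adverse event related to the monitoring carried out as part of" CADOM, and gives the TMG the task of advising the sponsor on continuing or stopping. Section 6.12.4.4.2 says "The TMG will review serious clinical incidents associated with MRI scanning and adverse events described in 6.13.3.1 to" look for trends and advise. There is no section 6.13.3.1; 6.12.3.1 is evidently meant. No interim analysis is planned (6.12.2) and there is no data monitoring committee (6.12.4.4.3).

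After remission, 6.7.4 says of participants: "They will be transferred into a less restrictive off-loading device and then finally into footwear as per standard care". Follow-up ends 6 months after remission.

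**The concern.** The safety list is presented as a subset of the recorded outcomes, but its falls entry is a different and smaller quantity. It leaves out any fall not put down to the device, including every fall once the participant is back in footwear. Serial MRI can do harm mainly by ending immobilisation too soon, and a fall in the newly mobilised period is one way in which that could show.

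The restriction also ties the listed count to two things other than fall risk. One is time in the device, which the intervention is meant to shorten. The other is an opinion on the cause of the fall. The protocol names no assessor for this, and 6.10.2 says that the trial cannot be blinded.

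At stake is whether the TMG would notice an excess of falls in footwear in one arm while the trial is running.

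**Working it through.** The protocol states no fall rate, expected fall count or weaning time, so there is no figure of its own to reproduce. The main check is a comparison of texts.

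**1. Scope of falls by section**

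- 6.5.2: all falls, graded, at each study visit.
- 6.6: any fall, through follow-up.
- 6.11.4.2: all falls, whole study.
- 6.12.3.1: only falls caused by the device.

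The last differs from the other three, although 6.12.3.1 says that it lists recorded outcomes.

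**2. Other routes to the TMG**

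- 6.12.3 covers events related to the trial's monitoring. A fall in footwear qualifies only if someone judges it to be so related.
- 6.12.4.4.2 covers MRI incidents and the listed events.

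Neither expressly brings in falls in footwear.

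**3. Illustration on assumed inputs**

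From the protocol: 30 per arm (6.8); follow-up to 6 months after remission (6.7.4); Arm B remission at 9 months, the lower end of the UK median range in 5.1.

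Assumed: Arm A remission at 6 months; weaning in a device for w = 0, 1 or 3 months, the same in both arms; r = 0.10 falls per person-month in device and footwear alike; every fall in a device is attributed to it.

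With R the month of remission, device months are D = R + w, footwear months F = 6 − w, and observed months T = R + 6. Listed falls = 30 × r × D, omitted falls = 30 × r × F, and omitted share = F/T.

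| w | D, A v B | Listed, A v B | Ratio | Omitted, A v B | Share omitted, A v B |
|---|---|---|---|---|---|
| 0 | 6 v 9 | 18 v 27 | 0.67 | 18 v 18 | 50% v 40% |
| 1 | 7 v 10 | 21 v 30 | 0.70 | 15 v 15 | 42% v 33% |
| 3 | 9 v 12 | 27 v 36 | 0.75 | 9 v 9 | 25% v 20% |

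All falls: 30 × 0.10 × 12 = 36 v 30 × 0.10 × 15 = 45, ratio 0.80. Per person-month: 36/360 = 0.10 v 45/450 = 0.10, ratio 1.00. Taking r from 0.05 to 0.20 halves or doubles the counts and leaves the ratios and shares unchanged.

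**4. What the list would not show**

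Take w = 1 and let the footwear rate in Arm A alone be 1.5 times higher, 0.15. Footwear falls become 30 × 0.15 × 5 = 22.5 v 15. The listed count stays at 21 v 30. All falls are 21 + 22.5 = 43.5 v 45, which still looks level. Per person-month they are 43.5/360 = 0.121 v 0.100, and only this form shows the excess.

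**5. How firm the direction is**

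With w = 0 and 6 v 9 device-months, the Poisson probability that Arm A still has at least as many listed falls as Arm B is about 0.20, 0.10 and 0.03 at r = 0.05, 0.10 and 0.20. With equal device time the expected ratio is 1.00; with 10 v 9 months it is 10/9 = 1.11.

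**The case against.** A reader might infer that Arm A must have fewer countable falls by definition, so that the falls comparison is biased in its favour. The protocol does not support that:

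- Shorter device time is the hypothesis under test. Arm A scans come only at 3, 6, 9 and 12 months, so earlier exit is not assured.
- A device is still worn during weaning, so device time does not stop at remission.
- The planned outcome is all falls. Nothing in the protocol uses the device-attributed count to compare the arms.

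A reader might also calculate that Arm A spends a much larger share of the first 12 months in footwear. That contrast comes from stopping the clock at 12 months. With follow-up to 6 months after remission and equal weaning, participants who reach remission have the same footwear time, 6 − w months, in either arm.

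It can fairly be added that the entry is a category of device harm, listed beside skin lesions from the device. Fewer such falls because the device is worn for less time would be a real gain. New ulcers, ulcer infection, amputation and worse pain are on the list with no device condition. The TMG's terms of reference, which are not shown, may widen what it sees.

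These points remove the claim of bias in the final comparison and lower the severity. They do not supply an entry for falls in footwear. The terms of reference might, but the protocol's own list should not depend on that.

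**Conclusion.** The mismatch is real and minor. The falls entry in 6.12.3.1 is narrower than the outcome it is said to repeat, and falls in footwear are on no list that the protocol expressly sends to the TMG. What the TMG would see depends on device time and on an unblinded opinion of cause.

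The gap affects only safety review during the trial, because the data for a full comparison at the end are collected at every visit. The sizes in the working depend on assumed remission times, weaning times and fall rates; they show how the list behaves and do not estimate what will happen in this trial. In an unpowered feasibility trial of 60, no firm inference on falls is expected in any case.

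**What to change.** In 6.12.3.1, replace the entry with: *All falls, any cause, graded on the Hopkins scale*. Report it to the TMG by arm from the existing eCRF data, with person-time at risk. Person-time is needed because follow-up length depends on the date of remission, and participants not in remission at 12 months leave the study (6.4.2). Raw all-falls counts would therefore still differ at equal risk (0.80 in the illustration). Record the device or footwear worn at the time of each fall as a descriptor, not as a condition for counting. Correct the cross-reference in 6.12.4.4.2 in the same amendment.

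The cost is one line of text, one descriptor field and a few more events in the TMG listing. No clinical procedure changes.

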6.12.3.2 Procedures to follow in the event of female participants becoming pregnant

In the event of a female participant becoming pregnant they have the option to withdraw from the trial. All participants who become pregnant will be excluded from the X-ray at 6 months post remission.

6.12.4 Quality Assurance and Control

6.12.4.1 Risk Assessment

The Quality Assurance (QA) and Quality Control (QC) considerations for the CADOM are based on the standard NCTU Quality Management Policy that includes a formal Risk Assessment, and that acknowledges the risks associated with the conduct of the trial and proposals of how to mitigate them through appropriate QA and QC processes. Risks are defined in terms of their impact on: the rights and safety of participants; project concept including trial design, reliability of results and institutional risk; project management; and other considerations.

QA is defined as all the planned and systematic actions established to ensure the trial is performed and data generated, documented and/or recorded and reported in compliance with the principles of GCP and applicable regulatory requirements. QC is defined as the operational techniques and activities performed within the QA system to verify that the requirements for quality of the trial related activities are fulfilled.

6.12.4.2 Central Monitoring at NCTU

NCTU staff will review Case Report Form (CRF) data for errors and missing key data points. The trial database will also be programmed to generate reports on errors and error rates. Essential trial issues, events and outputs, including defined key data points, will be detailed in the CADOM trial Data Management Plan.

6.12.4.3 On-site Monitoring

The frequency, type and intensity of routine and triggered on-site monitoring will be detailed in the CADOM Quality Management and Monitoring Plan (QMMP). The QMMP will also detail the

procedures for review and sign-off of monitoring reports. In the event of a request for a trial site inspection by any regulatory authority, NCTU must be notified as soon as possible.

6.12.4.3.1 Direct access to participant records

Participating investigators must agree to allow trial related monitoring, including audits, REC review and regulatory inspections, by providing access to source data and other trial related documentation as required. Participant consent for this must be obtained as part of the informed consent process for the trial.

6.12.4.4 Trial Oversight

Trial oversight is intended to preserve the integrity of the trial by independently verifying a variety of processes and prompting corrective action where necessary. The processes reviewed relate to participant enrolment, consent, eligibility, and allocation to trial groups; adherence to trial interventions and policies to protect participants, including reporting of harms; completeness, accuracy and timeliness of data collection; and will verify adherence to applicable policies detailed in the Compliance section of the protocol. Independent trial oversight complies with the NCTU trial oversight policy.

In multi-centre trials this oversight is considered and described both overall and for each recruiting centre by exploring the trial dataset or performing site visits as described in the CADOM Management and Monitoring Plan.

6.12.4.4.1 Trial Management Team

The Trial Management Team (TMT) will be set up to assist with developing the design, co-ordination and day to day operational issues in the management of the trial, including budget management. The membership, frequency of meetings, activity (including trial conduct and data review) and authority will be covered in the TMT terms of reference.

6.12.4.4.2 Trial Management Group

A Trial Management Group (TMG) will be set up to assist with developing the design, co-ordination and strategic management of the trial. The membership, frequency of meetings, activity (including trial conduct and data review) and authority will be covered in the TMG terms of reference.

The TMG will review serious clinical incidents associated with MRI scanning and adverse events described in 6.13.3.1 to

- Detect any trends, such as increases in un/expected events, and take appropriate action
- Provide advice to the CI to when to seek information from investigators where required
- Provide advice to Sponsors on the risk of the trial continuing and take appropriate action where necessary

6.12.4.4.3 Independent Data Monitoring Committee

CADOM is a feasibility trial with no planned interim analyses. The intervention is low risk thus no DMC is required.

6.12.4.4.4 Trial Sponsor

The role of the sponsor is to take on responsibility for securing the arrangements to initiate, manage and finance the trial. When an institution is the trial sponsor and has delegated some and/or the totality of Sponsor's responsibilities to the NCTU, the Sponsor's form for delegated responsibilities should be completed and signed by all parties before the start of the trial.

7 Ethics and Dissemination

7.1 Research Ethics Approval

Before initiation of the trial at any clinical site, the protocol, all informed consent forms and any material to be given to the prospective participant will be submitted to the relevant REC for approval. Any subsequent amendments to these documents will be submitted for further approval. Before initiation of the trial at each additional clinical site, the same/amended documents will be submitted for local Research and Development (R&D) confirmation of capacity and capability.

The rights of the participant to refuse to participate in the trial without giving a reason must be respected. After the participant has entered the trial, the clinician remains free to give alternative treatment to that specified in the protocol, at any stage, if s/he feels it to be in the best interest of the participant. The reasons for doing so must be recorded. After randomisation the participant must remain within the trial for the purpose of follow up and data analysis according to the treatment option to which they have been allocated. However, the participant remains free to change their mind at any time about the protocol treatment and follow-up without giving a reason and without prejudicing their further treatment.

